12.2 Subject Confidentiality

Confidentiality will be maintained by following the data collection and management plans described previously in the protocol. Additionally, we will provide each participant with a study ID number that will be used to code all collected data. Participant information will be de-identified and will not be linked to any specific subject. Only key research personnel will have access to all collected data. All identifiers will be destroyed upon completion of the study.

12.3 Unanticipated Problems

Any unanticipated problems experienced by study personnel will be reported to the PI and co-PI. The PI and co-PI will then report any problems to the IRB, and National Institutes of Health, as necessary.

Improving Health by Linking Postpartum and Well-Baby Visits: Administrative Supplement to LINCC Trial

Project Summary/Abstract

Severe maternal morbidity (SMM) and maternal mortality (MM) remain a public health crisis in the United States despite efforts to improve maternal health. Most pregnancy-related deaths in the U.S. occur in the postpartum (PP) period, thus, timely access to high quality comprehensive care during the transition period from prenatal to PP period is critical to reduce SMM and MM.

High quality longitudinal health care improves outcomes for women before, during and after pregnancy; and decreases morbidity and mortality related to pregnancy. The “Linking Inter-professional Newborn and Contraception Care (LINCC) Trial” was funded in 2019 to test a novel, patient-centered approach to providing contraception care, in conjunction with an infant’s well baby visit (WBV), for PP women. The LINCC trial aims to remove barriers to accessing PP care by co-scheduling the PP contraception visit with WBVs. The LINCC trial provides an ideal foundation upon which to develop a reproducible model to identify women at risk for MM and SMM, and link them into care, among a national sample of predominantly low-income women receiving care at Community Health Centers (CHCs).

The specific aims of this study are to: (1) build a population-health interface to identify pregnant and PP women at risk for SMM or MM using standard clinical health data from electronic medical records and (2) Validate the registry (i.e., LINK MOMS) using data from CHCs across the country. Lastly, we aim to: (3) design an implementation plan for the LINK MOMS registry in CHCs across the country.

Increasing access to timely comprehensive care is a promising strategy to prevent pregnancy-related morbidity and mortality. The long-term impact of this study is to reduce adverse health outcomes among PP women by increasing access to patient-oriented care before, during, and after pregnancy. Findings may provide evidence supporting a paradigm shift for linked PP care and identify important insights to facilitate successful implementation of this registry in health care systems across the nation.

Background/Scientific Rationale

Maternal Morbidity and Mortality in the United States: Severe maternal morbidity (SMM) and maternal mortality (MM) in the U.S. remains a public health crisis despite efforts to improve maternal health. Given most pregnancy-related deaths in the U.S. occur in the postpartum (PP) period[1], a critical preventive measure to SMM and MM is timely access to quality health care during the transition between the prenatal period to one year PP.

Importance of Continuum of Care for PP Women: Standard clinical practice, i.e. a single PP visit approximately six weeks after delivery, fails to provide adequate care for women, particularly for those at risk for SMM or MM. Indeed, many women, particularly low-income minority women, do not present for the traditional PP visit [3]. In fact, prior analyses of Illinois Medicaid data by our team, and an analysis of California Medi-Cal data, found PP visit rates to be 56% and 49.4% (respectively) [4, 5]. Because the majority of maternal deaths occur between 6-weeks to 12-months after delivery, the need for a continuum of care that extends beyond the traditional 6-week period is essential to improve outcomes for new mothers [6]. In May 2019, The American College of Obstetricians and Gynecologists' (ACOG) reported that PP care should be an on-going process with the timing of visits scheduled to address woman's individual needs, including recovery from birth, newborn care, psychosocial and sexual well-being, contraception, chronic disease management, and transition to ongoing well-woman care[7]. Unfortunately, this proposed continuum of PP care has not yet been adopted broadly across the U.S.

Disparities in Access to Quality Maternity Care: Access to quality maternity care is a critical component of positive maternal health outcomes, especially within the PP period as most complications occur within this period. However, research has indicated that access to reproductive health care and health insurance continues to be a barrier for women [8]. Although disparities in the rates of uninsured have narrowed among some populations [9], gaps do remain, particularly for low-income and minority women [10]. For instance, while an average of 13% of adult women in the U.S. are uninsured, the percentages are greater for Black (15%), Latina (24%), and low-income women (26%)[10]. In addition, uninsured women use fewer preventative services (e.g., mammograms, well-woman visits) and are more likely to delay care due to cost [11]. Thus, increasing prevalence of chronic disease risk factors [12], coupled with inadequate care due to cost or delays, puts low-income and minority women at an high risk for adverse maternal health outcomes.

Other key factors contributing to poor access to care include geographic disparities (e.g., distance to care, transportation needs) [6, 13]. Compared to those living in urban areas, women living in rural areas experience disparities in obstetric care access and outcomes [14]. In fact, maternal and infant mortality rates in most rural areas of the U.S. are measurably higher than those in large metropolitan areas [15]. Furthermore, research suggests that risk factors for related chronic diseases such as diabetes, high cholesterol,

and cardiovascular disease are becoming more prevalent in women of reproductive age [12], with the burden of these conditions disproportionality falling on women in rural or low-income communities [16]. Given more than 18 million women of reproductive age live in rural counties of the U.S., and nearly half a million women give birth each year in rural hospitals [17, 18], ensuring access to maternity care for all women has the potential to reduce preventable maternal mortality and morbidity across the U.S. and improve maternal outcomes overall.

Community Health Centers (CHCs) serve as a safety net for underserved urban and rural residents [19]. Research has shown that 83% of individuals who receive care at CHCs have a form of public insurance or no insurance, while only 39% of patients who seek care at private physician offices are uninsured or have public forms of insurance [20] Overall, CHCs serve an estimated 24% of all low-income women of childbearing age in the U.S. [24]. Therefore, CHCs can serve as an ideal setting to identify women at risk for poor pregnancy-related outcomes.

Optimize Linkage to Continued Care – Leveraging the “Linking Inter-professional Newborn and Contraception Care (LINCC)” Trial: A crucial approach to preventing pregnancy-related morbidity and mortality is to provide women-centered approaches to improve timely access to comprehensive care before, during and after pregnancy. The LINCC Trial was funded in 2019 to test a novel, woman-centered approach to providing contraception in conjunction with an infant’s well baby visit (WBV) to PP women. This intervention aims to remove barriers to accessing PP care by co-scheduling the PP care with WBVs. The LINCC model allows women greater opportunity to receive timely PP contraception, space pregnancies, and decrease the risk of a rapid repeat pregnancy within a short inter-pregnancy interval which is associated with poor maternal and infant outcomes. The LINCC Trial provides an ideal platform for a larger paradigm shift in PP care: ensuring a continuum of care throughout the pregnancy and interception period. Comprehensive women’s health care, including PP care, preventive care, chronic disease management and mental health care, is desperately needed to address rising SMM and MM, especially among underserved vulnerable women. By leveraging our existing community partnership with AllianceChicago as well as our clinical champions at participating CHCs engaged in the ongoing LINCC Trial, we will build a population-health approach to identify women at highest risk for maternal morbidity and mortality.

Impact of the Research: Most pregnancy-related deaths in the U.S. occur in the PP period [1], however the traditional model for PP care is inadequate in identifying women at risk for SMM and MM; and inadequate in addressing maternal health needs in the inter-conception period [3]. The fragmentation of the current healthcare system leads to inadequate linkage between health care services, specifically for women at highest risk for adverse health outcomes [21, 22]. Early identification of women who are at risk for SMM or MM will lead to earlier management of chronic conditions and prevention of pregnancy-related complications.

Study Design Background

The “Improving Health by Linking Postpartum and Well-Baby Visits (LINCC Trial)” was funded in 2019 to test a novel, patient-centered approach to providing contraception care, in conjunction with an infant’s well baby visit (WBV), for postpartum (PP) women. The impetus for the LINCC Trial was to improve outcomes for women at greatest risk for poor pregnancy-related outcomes: low-income and minority women. The LINCC Trial is reducing barriers to receipt of PP contraception care by linking women’s care with newborn care. The LINCC model allows women greater opportunity to receive timely PP contraception, space pregnancies, and decrease the risk of a rapid repeat pregnancy within a short interpregnancy interval which is associated with poor maternal and infant outcomes. Thus, the LINCC Trial is an ideal foundation upon which to further develop a reproducible model to identify pregnant and postpartum women at risk for severe maternal morbidity (SMM) and maternal mortality (MM) among a national sample of federally qualified health centers and respond to the goals of the administrative supplement.

The specific aims of this study are to:

- 1) Build a population-health interface to identify pregnant and PP women at risk for severe maternal morbidity or mortality using standard clinical health data from electronic health records and create a LINK MOMS registry;
- 2) Validate the LINK MOMS registry using data from Community Health Centers (CHCs) across the country;
- 3) Design an implementation plan for the LINK MOMS registry in CHCs across the country. This supplement aims to bridge the gap in care during a critical time, the PP period, by identifying women at increased risk of SMM and MM.

The LINCC Trial provides an ideal platform for a larger paradigm shift in PP care: ensuring a continuum of care throughout the pregnancy and interception period. By leveraging our existing community partnership with AllianceChicago, as well as our clinical champions engaged in at participating CHCs, from the ongoing LINCC Trial, we will build a population-health approach to identify women at highest risk for maternal morbidity and mortality with the long-term goal of providing improved linkage to care.

The following text will outline the study activities for Aims 1, 2, and 3 of this Administrative Supplement.

Aim 1: Build a population-health interface to identify pregnant and PP women at risk for severe maternal morbidity or mortality using standard clinical health data from electronic health records (EHR).

In partnership with AllianceChicago, we will use Health Catalyst's Population Builder™ to build a registry to identify pregnant and PP women at risk for SMM or MM. Though many women do not receive timely or adequate PP care, nearly all women receive at least some medical care during pregnancy [23]. We hypothesize that medical record data, even if limited, can be used for early identification of women at highest risk for SMM and MM and will result in earlier intervention and improved health outcomes.

Health Catalyst Population Builder™ is a tool designed to interface with large datasets, including medical records, to develop robust registries based on pre-specified criteria. Importantly, Population Builder™ is end-user friendly through the use of visually-oriented data, a drag-and-drop interface, rapid identification of desired populations and flexibility to be used in many domains (clinical, financial, and geographic). Nontechnical individuals can easily learn to use the tool, which allows for rapid access to desired data by clinical staff.

Focus group subjects will be assigned a study ID during the course of the study. All data collected will use the participant's study number in place of identified information. Participant information will be de-identified and will not be linked to any specific subject. The consent forms will be the only remaining link to the subjects. They will be available only to the research team. Consent forms for the subjects will be securely stored in a locked filing cabinet in a locked RUMC office. All data will be stored on a secure, password-protected computer accessible only to the study team.

Both focus group sessions will take place virtually over the Zoom platform and be audio-recorded and transcribed. Qualitative data will be coded independently by two coders and then discussed to resolve coding discrepancies. Emerging themes will be identified and categorized as components of the registry. All sessions will be reviewed carefully by the PIs to determine clinically relevant aspects particular to ensuring successful registry development.

- Each focus group session is expected to take approximately 1 hour
- Each participant will receive \$100 gift card after participating in each session for a total of \$200. (Per benchmark standard for clinicians [hourly rate = \$100])

Retrospective Chart Review

In addition, once the LINK MOMS metrics are defined and built; the registry will be tested nationally using 32 CHCs affiliated with AllianceChicago. During the test phase the registry will be limited to electronic health record (EHR) data from 2017-2019. This time frame allows for the validation process to include review of care after delivery. This retrospective chart review will be conducted to test the registry. Data will be collected on all pregnant or postpartum women attending the 32 CHCs affiliated with AllianceChicago.

The chart will be reviewed to ensure the registry is accurately identifying women at risk of adverse health outcomes during pregnancy and the postpartum period.

Retrospective Chart Review Criteria

Approximately 1000 charts will be included in the retrospective chart review period from 2017-2019.

Inclusion Criteria

- Pregnant or postpartum women of reproductive age attending an appointment at an AllianceChicago affiliated CHC between 2017-2019.

Exclusion Criteria

- Pregnant or postpartum women of reproductive age attending an appointment at a health clinic not affiliated with AllianceChicago
- Pregnant or postpartum women of reproductive age attending an appointment at an AllianceChicago affiliated CHC outside of the 2017-2019 date range

Data Collection and Management Procedures

The AllianceChicago study team and SMEs will test the LINK MOMS registry using data from CHCs within AllianceChicago's network. Data from this retrospective chart review process will be securely stored at AllianceChicago Office. The RUMC and UIC teams will oversee the testing process and provide insight where applicable. De-identified data may be shared between sights for this aim of the study.

A reliance request on behalf of AllianceChicago and UIC has been approved and is being submitted via amendment to RUMC's IRB for final approval. Once approved, the RUMC IRB will be the IRB of Record. Additionally, de-identified data from this study will be shared between collaborating sites (i.e., RUMC, UIC, AllianceChicago). Confidentiality agreements and a data sharing agreement will be submitted and approved prior to any data being shared between sites.

The first focus group session for Aim 1 has been completed. The second focus group will be conducted in Fall 2021. The variables and metrics for the registry are currently being defined and built by the study team. The registry is on track to be built and ready for testing and validation in September 2021.

Aim 2: Validate the LINK MOMS registry using data from CHCs across the country.

To ensure the registry accurately identifies women at risk for SMM and MM, AllianceChicago SMEs in conjunction with SMEs across a sub-set of clinical sites will validate the national LINK MOMS registry through a manual review of patient-level EHR data (i.e., retrospective chart review). A random sample of 15% of women from the LINK MOMS registry will be pulled for validation. The validation process will include a manual review of each patient's chart and discussion with treating clinicians if appropriate. The

chart review will include all clinical data 2017-2019, which will include the timeframe during and after pregnancy. A structured chart abstraction tool will be used to standardize the review process; and each abstraction will result in one of three outcomes: Appropriate, Inappropriate, Unknown. Our team will meet with the validation team weekly during the validation process to review findings and refine the validation methodology as needed.

Retrospective Chart Review Criteria

Approximately 15% of the 1000 charts (Aim 1) will be included in the retrospective chart review period from 2017-2019.

Inclusion Criteria

- Pregnant or postpartum women of reproductive age attending an appointment at an AllianceChicago affiliated CHC between 2017-2019.

Exclusion Criteria

- Pregnant or postpartum women of reproductive age attending an appointment at a health clinic not affiliated with AllianceChicago
- Pregnant or postpartum women of reproductive age attending an appointment at an AllianceChicago affiliated CHC outside of the 2017-2019 date range.

Data Collection Analysis

The chart abstraction process will include documentation of details supporting the final outcome (Appropriate, Inappropriate, Unknown). For example, the registry identifies a chart with a one-time use of ICD-10 code 013.9 (gestational hypertension). However, upon chart review the documented blood pressure measurements were found to be normal during pregnancy. Thus, the team concludes the use of the code was likely an error and the chart is labelled as an inappropriate identification of risk. Similarly, the team may find conflicting data in the EHR and the chart is labelled as an unknown identification of risk.

All charts found to be unknown or inappropriate will be reviewed by the validation team and PIs ([name], [name]) and the group will reach consensus on the final determination (Appropriate, Inappropriate or Unknown). If needed, the team will engage the woman's care providers to accrue additional information. All findings will be compiled and used to continually refine the LINK MOMS registry. An example of such a registry refinement process would be if the team determines, based on the chart abstraction, that certain ICD codes need to be documented more than once for the chart to be pulled into the registry.

The AllianceChicago study team and SMEs will validate the LINK MOMS registry using data from CHCs within AllianceChicago's network. Data from this retrospective chart review and validation process will be securely stored at AllianceChicago Office. The RUMC and UIC team will oversee the validation process and provide insight where applicable. De-identified data may be shared between sights for this aim of the study.

Aim 3: Design an implementation plan for the LINK MOMS registry in CHCs across the country.

Key Informant Interviews

Through in-depth key-informant interviews, we will use the guidance from women and women's health providers to develop a strategy for how best to incorporate LINK MOMS data into practice.

Inclusion Criteria

- **Patients:** Pregnant or postpartum (delivery within last 12 months) women (ages 18 and above) receiving care at an affiliated CHC in AllianceChicago network
- **Providers:** English or Spanish-speaking women's health provider at affiliated CHC (ages 18 and above)

Exclusion Criteria

- **Patient:** Not a pregnant or postpartum women receiving care at an affiliated CHC in AllianceChicago's network (under 18 years old)
- **Providers:** Not a women's health provider at affiliated CHC in AllianceChicago's network (under 18 years old)

Subject enrollment:

The key informant interviews will be conducted by a member of our research team using a semi-structured interview guide to ensure consistency of data collection while allowing for open-ended responses. Questions and prompts will be developed to solicit information; which will be closely reviewed by the PIs before conducting interviews. Participation will be voluntary.

- **Patient:** The study team will coordinate with the CHC's to facilitate recruitment of eligible participants for the key informant interviews. Staff at each CHC will hand out study flyers to recruit patients. Interested patients will reach out to the study team using the contact information on the flyers. A trained research assistant will determine eligibility and coordinate a time with the patient to participate in the interview by phone. The research assistant will consent eligible patients prior to participating in the interview. Those interested and eligible will complete an oral informed consent form and be enrolled in the study. All participants will have their participation and all risks and benefits to participation explained to them.
- **Providers:** The study team will coordinate with the CHC's and facilitate recruitment of eligible participants for the key informant interviews. A trained research assistant will determine eligibility and coordinate a time with the providers to participate in the interview by phone. The research assistant will consent eligible providers prior to participating in the interview. Those interested and eligible will complete an oral informed consent form and be enrolled in the study. All participants will have their participation and all risks and benefits to participation explained to them.

- Each interview (patient and provider) is expected to take approximately 30 minutes.
- Each patient participant will receive \$25 gift card after participating in one interview.
- Each provider participant will receive \$50 gift card after participating in one interview (Per benchmark standard for clinicians [hourly rate = \$100]).

Women's Voices: We will recruit 10 women who are pregnant or PP (delivery within last 12 months) to participate in an interview by phone. Interviews will focus on women's preferences and needs regarding care, feedback on the LINK MOMS registry, suggestions for how the registry should be used to identify and link women to needed care, and concerns regarding privacy.

Provider's Voices: We will recruit 10 women's health providers who provide pregnancy and/or PP care. We aim to recruit a variety of providers with varying backgrounds and perspectives (OB/GYN, Family Medicine, Nurse Midwife and Internal Medicine). Interviews will focus on clinician's preferences regarding how registry data is utilized in clinical practice, barriers and facilitators to utilization of LINK MOMS and any resource considerations.

Aim 3a: Evaluate usability of LINK MOMS registry

Survey

A qualified study team member will disseminate a survey via REDCap to evaluate the usability and usefulness of the LINK MOMS registry. The 8-question deidentified survey will be sent to the 20 emails of health providers who currently use the registry.

Data Analysis

Data analysis: All interviews will be audio-recorded and transcribed. Data will be coded independently by two coders and then discussed to resolve coding discrepancies. Emerging themes will be identified and categorized as important considerations for an implementation plan for the LINK MOMS registry. All interviews will be reviewed carefully by both PIs to determine relevant aspects particular to ensuring successful implementation development.

Data Collection and Management Procedures

We will collect qualitative and quantitative data from participants via audio-recorded and transcribed key informant interviews administered virtually.

Interview subjects will be assigned a study ID during the course of the study. All data collected will use the participant's study number in place of identified information. Participant information will be de-identified and will not be linked to any specific subject. The consent forms will be the only remaining link to the subjects. They will be available only to the research team. Consent forms for the subjects will be securely stored in a locked filing cabinet in a locked RUMC office. All data will be stored on a secure,

password-protected computer accessible only to the study team.

Clinic-level EHR data collected retrospectively as part of the testing process in Aim 1 and validation process in Aim 2 will be stored securely at AllianceChicago Office.

A reliance request on behalf of UIC and AllianceChicago was approved in July 2021. This reliance agreement is being submitted to RUMC's Institutional Review Board (IRB) and once approved, the RUMC's IRB will be the IRB of Record. Additionally, de-identified data from this study will be shared between collaborating sites (i.e., RUMC, UIC, AllianceChicago). Confidentiality agreements are in place and a data sharing agreement will be submitted and approved prior to any data being shared between sites.

Quality Control and Quality Assurance

Analysis of each phase will help to ensure adherence to the protocol as well as informing the next phase of the research project. The co-investigators are all responsible for ensuring the quality of the data and how the analysis will inform the next phase of the research study.

Data and Safety Monitoring

The PIs and Co-I are responsible for monitoring the data, assuring protocol compliance, and conducting safety reviews regularly. The research staff will oversee day-to-day compliance. This protocol presents minimal risks to the subjects and adverse events or other problems are not anticipated. The PIs, Co-I, and research staff will be responsible for monitoring the data, assuring protocol compliance, and conducting safety reviews at regular intervals, which must be conducted at a minimum of every 6 months (including when re-approval of the protocol is sought). During the review process, the PIs, Co-Is and research staff will evaluate whether the study should continue unchanged, require modification/amendment, or to close enrollment. The PIs, Co-I, IRB, and research staff will ensure that any deviations from the protocol or safety concerns are reported according to institutional guidelines. Data and study risk will be assessed throughout the study.

Informed Consent

Focus group sessions (Aim 1): A qualified member of the study team will conduct eligibility screening to ensure participant eligibility in focus group sessions. Eligible participants will be complete oral consent over the phone and be enrolled. Recruitment will take place at AllianceChicago and participating CHC sites. The oral informed consent process will inform the participant that participation in the study is completely voluntary.

Retrospective chart review (Aim 1 and 2): The study team is requesting a waiver of consent process and consent documentation for the retrospective chart reviews in Aims 1 and 2.

Key informant interviews (Aim 3): A qualified member of the study team will conduct eligibility screening to ensure participant is eligible to participate in the key informant interview. Eligible participants (providers and patients) will complete oral consent over the phone and be enrolled. Recruitment will take place at AllianceChicago and participating CHC sites. The oral informed consent process will inform the participant that participation in the study is completely voluntary.

Survey (Aim 3a): No identified data will be obtained. Therefore, a Waiver of Documented Consent will be submitted.

Subject Confidentiality

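### The LINK MOMS chart review uses 2017-2019 both to select women and to limit the records read, so care during and after pregnancy cannot be fully reviewed for some eligible women

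*Combined protocol and SAP*

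**What the plan says.** Everything here is in the Administrative Supplement (LINK MOMS).

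- **Data window, Aim 1, Retrospective Chart Review.** "During the test phase the registry will be limited to electronic health record (EHR) data from 2017-2019". The reason given is: "This time frame allows for the validation process to include review of care after delivery".
- **Data window, Aim 2.** The "chart review will include all clinical data 2017-2019, which will include the timeframe during and after pregnancy".
- **Inclusion, the same in Aims 1 and 2.** "Pregnant or postpartum women of reproductive age attending an appointment at an AllianceChicago affiliated CHC between 2017-2019". A matching exclusion removes women whose appointment at an affiliated centre lies outside those years.
- **Size.** "Approximately 1000 charts will be included in the retrospective chart review period from 2017-2019". Aim 2 validates about 15% of these.
- **Horizon.** The Background asks for "timely access to quality health care during the transition between the prenatal period to one year PP" and states that "the majority of maternal deaths occur between 6-weeks to 12-months after delivery". The chart review criteria do not define postpartum. A 12-month definition appears only for people to be interviewed, in the Aim 3 patient criteria ("Pregnant or postpartum (delivery within last 12 months) women (ages 18 and above") and the Aim 3 recruitment text.
- **Use of the result.** Under Aim 2, each chart is labelled Appropriate, Inappropriate or Unknown. The findings are used to refine the registry rules, for example by requiring certain codes to appear more than once.

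**The concern.** One calendar window does two jobs. It decides who is in the sample and how much of each woman's record may be read. Because both uses end on 31 December 2019, a woman seen for prenatal care in December 2019 qualifies, but her delivery and postpartum care fall outside the readable record. A woman who delivered in October 2019 has at most three months. At the other end, a woman seen postpartum in January 2017 has no pregnancy record in the window.

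At stake is whether the validation can do the post-delivery review that the plan gives as its reason for choosing these years. A flag raised by a postpartum condition, or by a pregnancy that ended before 2017, may have to be judged without the records that would confirm or refute it. The judgements then feed into the registry rules.

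**Working it through.** The plan gives no figure for completeness of follow-up, so there is none to reproduce. The check is a window-overlap calculation.

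**Inputs from the documents:** a window of 3 years; about 1,000 charts; 15% validated, so 0.15 × 1,000 = 150; a 12-month horizon from the Background.

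**Assumptions (not in the documents):** delivery dates are uniform over time. A woman is eligible if her care span, from *g* years before delivery to *p* years after, overlaps 2017-2019. *g* is 39, 30 or 20 weeks (0.75, 0.577, 0.385 years). *p* is 6, 12 or 52 weeks (0.115, 0.231, 1 year). The required follow-up *h* is 6, 12 or 52 weeks, no longer than *p*.

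**Formulas.** Eligible delivery dates span T = 3 + *g* + *p* years.
- No postpartum data (delivery after 2019): *g*/T
- Some, but less than *h*: *h*/T
- Delivered before 2017: *p*/T
- Whole care span before delivery and *h* after it in the window: (3 − *h* − *g*)/T

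**Base case** (*g* = 0.75, *p* = *h* = 1; T = 4.75):
- No postpartum data: 0.75/4.75 = 15.8%
- Cut short of 12 months: 1/4.75 = 21.1%
- Either: 1.75/4.75 = 36.8%, or 368 of 1,000 charts and 150 × 0.368 = 55 validation charts
- Delivered before 2017: 1/4.75 = 21.1%
- Pregnancy and 12 months postpartum both in the window: (3 − 1 − 0.75)/4.75 = 26.3%

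**Range over the assumptions:**

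| Share of charts | Lowest | Highest |
|---|---|---|
| No postpartum data | 0.385/4.385 = 8.8% | 0.75/3.865 = 19.4% |
| Short of 6-12 weeks | (0.385 + 0.115)/4.385 = 11.4% | (0.75 + 0.231)/3.981 = 24.6% |
| Short of 12 months | (0.385 + 1)/4.385 = 31.6% | (0.75 + 1)/4.75 = 36.8% |

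**Visit-based check.** A simulation made eligibility depend on an actual visit in the window. It assumed a prenatal schedule with entry to care between weeks 8 and 20. Six-week attendance was 49.4% or 56% (the two rates in the Background) or 100%, with or without a later visit. It gave 11.5%-13.2% with no postpartum data, 14.4%-19.7% short of 6-12 weeks, and 36.4%-41.6% short of 12 months. The last result widens the 12-month range to about 32%-42%.

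**Simple cross-check.** Counting only deliveries inside the window, the 12 delivery months of 2019 out of 36 (33%) lack a full postpartum year.

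**The case against.** The strongest reply is that Aim 2 asks whether a risk flag is correct, not whether an outcome followed. A woman with no postpartum data can be flagged only on records inside the window, and the records around that flag are usually there too. The plan's one worked example, gestational hypertension, is settled by blood pressures taken in pregnancy. Its illustration of Unknown is conflicting data, not missing follow-up. This stands for flags that rest on an in-window pregnancy. It does not cover postpartum flags near the end of 2019, or flags in early 2017 that rest on an earlier pregnancy.

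A reader might infer that truncated charts will be mislabelled and that these labels will distort the registry rules. The documents do not show this. Every chart labelled Unknown or Inappropriate goes to the validation team and the principal investigators for consensus, and care providers can be asked for more information. That contact is discretionary and tied to no follow-up requirement, so it reduces the problem without removing it.

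A reader might also call the two statements about the time frame simply false. They promise no full postpartum year for every woman, and they hold for many. They fail for women still pregnant at the end of 2019 and are only partly met for late-2019 deliveries.

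The size also depends on the horizon. Among deliveries inside the window, only those of October to December 2019 (3 of 36 months, 8%) have less than three months of follow-up. The 12-month horizon comes from the Background, not from the chart review criteria. That is why shorter horizons are shown as well.

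**Conclusion.** The point holds as a limit on what the validation can examine. With inclusion and readable data sharing the same three years and no delivery-date rule, the stated review of care during and after pregnancy is impossible for some eligible women and incomplete for others. The affected share is about 9%-19% with no postpartum data, 11%-25% short of 6-12 weeks, and 32%-42% short of 12 months (base case 37%). In addition, women who delivered before 2017 lack pregnancy data.

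These figures rest on evenly spread deliveries and assumed lengths of care. The count of 55 in 150 also assumes that the sampled charts have the same spread of delivery dates as all eligible women. The effect falls mainly on postpartum flags and on flags from a pre-2017 pregnancy. Bias in the labels remains a possibility, not a finding. The point concerns the supplement's registry validation only and does not touch the LINCC trial's primary outcome.

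**What to change.** 1. Keep 2017-2019 as the inclusion window. For the roughly 150 sampled validation charts, set a separate reading window from the start of the index pregnancy to 12 months after delivery, and change the dates in the consent-waiver request to match. On the base-case assumptions the extremes are about April 2015 (1 January 2017 less 1 year less 0.75 year) and the end of September 2021 (31 December 2019 plus 0.75 year plus 1 year). The registry was due to be ready for testing in September 2021, so nearly all the later records would exist by then. Whether records before 2017 can be reached is not stated and should be checked.
2. State that the exclusion for appointments outside 2017-2019 does not remove women who continued care into 2020. Read literally, it would.
3. Record the follow-up available for each chart, and report Appropriate, Inappropriate and Unknown separately for charts with complete and incomplete follow-up.
4. Do not restrict the sample to women with complete follow-up. The Background reports postpartum visit rates of only 56% and 49.4%, so a restriction could select out women lost to care, whom the registry is meant to find.

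The cost is slightly more chart reading per woman and a change to the waiver dates.
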